12.3. Level of statistical significance

Two-sided statistical testing will be performed throughout. A 5% level of statistical significance will be used for analyses of all outcomes.

12.4. Early trial cessation

A recommendation may be made by the Data Monitoring Committee to the Trial Steering Committee to stop the trial early following review of interim analysis or evidence from other relevant studies becoming available. Guidelines for the early cessation of the trial will be agreed with the DMC and documented in the DMC Charter.

12.5. Procedures for reporting deviations from the original statistical analysis plan All deviations from the original statistical analysis plan will be reported in the final report, as appropriate.

12.6. Economic evaluation

The economic evaluation will take the form of a cost-consequence analysis and will present outcomes and healthcare costs in a disaggregated manner for both mothers and their infants (Mauskopf, Paul et al. 1998). The perspective of the analysis will be of the NHS and the time-horizon will be a one-year time frame for infants and lifetime for mothers. However, we will also present a cost-utility analysis from the mother's perspective with a time-horizon up to 3 months.

Health outcomes at 3 months of age will include the primary outcome, the maternal anxiety and depression dimension of the EQ-5D-5L, overall health-related quality of life (EQ-5D-5L), and maternal and infant healthcare costs. Healthcare resource use categories using the online data capture platform will collect information on general practice visits and hospital admissions up to 3 months of age. These healthcare resource use categories will be weighted by appropriate unit costs obtained from national sources to estimate the costs in each trial arm (Curtis and Burns 2015, Department of Health 2015). For the within-trial analysis, maternal quality adjusted life days (QALDs) will be derived as the area under the

curve for the health profile created connecting health-related quality of life measures at one week post-intervention and then at 3 months follow-up. To estimate costs (or savings) in each arm of the trial beyond the trial end date, we will employ a validated published economic model (Pokhrel, Quigley et al. 2015). The model evaluates the potential cost savings attributable to increases in breastfeeding rates through different healthcare policies. We will use the observed treatment effect in the trial (breastfeeding rate difference at 3 months of age) and map such value into one of the policies explored in the economic model to extrapolate costs. For infants, we will extrapolate up to one-year follow-up healthcare costs (or savings) associated with gastrointestinal illness, lower respiratory tract infection and acute otitis media. For mothers, we will use the treatment effect to estimate the potential lifetime maternal healthcare costs (or savings) due to breast cancer. These categories of healthcare costs (at one year for infants and lifetime for mothers) will also be included in the cost-consequence analysis.

Mean health-related quality of life values, resource use and costs estimated using trial data will be accompanied with appropriate 95% confidence intervals. Uncertainty around extrapolated cost figures using the economic model will be dealt with using deterministic sensitivity analysis.

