- maternal health-related quality of life (EQ-5D-5L)
- maternal and infant NHS healthcare resource use
- To examine, through an alongside economic evaluation, whether any additional benefits associated with frenotomy are justified by any additional health care resources needed to deliver the intervention
- To investigate the effect of frenotomy on breastfeeding rates measured at six months.

Secondary outcome measured at 6 months:

· any breastmilk feeding

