Post-procedure adverse events (tongue cut*, scarring, salivary duct damage*): measured by specific questions

Maternal anxiety and depression dimension of EQ-5D-5L*

Maternal health-related quality of life: as elicited by the EQ-5D-5L*

To examine, through an alongside economic evaluation, whether any additional benefits associated with frenotomy are justified by any additional health care resources needed to deliver the intervention

Maternal and infant NHS healthcare resource use: collected at 3 months of age on general practice visits and hospital admissions

To investigate the effect of	Any breastmilk feeding at 6 months	At 6 months of age
frenotomy on breastfeeding rates	according to maternal self-report: defined	
measured at six months.	as any breastmilk feeding in the 24 hours	
	prior to the infant reaching six months of	
	age	

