- Maternal and infant NHS healthcare resource use: collected on general practice visits and hospital admissions

9.6.4. 6 month follow-up

The following data will be collected using maternal self-report (via web-link to data capture platform, telephone, email or post) when the infant is 6 months of age:

 Any breastmilk feeding at 6 months according to maternal self-report: defined as any breastmilk feeding in the 24 hours prior to the infant reaching six months of age

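### Section 12.6 builds each arm's costs from GP visits and hospital admissions and names no cost for the frenotomy, the resource the economic objective sets out to weigh

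*Protocol*

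**What the plan says.** The Synopsis and Section 6 give the economic objective as examining "whether any additional benefits associated with frenotomy are justified by any additional health care resources needed to deliver the intervention". Section 12.6 sets the viewpoint: "The perspective of the analysis will be of the NHS".

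The costing rule in Section 12.6 has two steps. The online platform "will collect information on general practice visits and hospital admissions up to 3 months of age". Then: "These healthcare resource use categories will be weighted by appropriate unit costs obtained from national sources to estimate the costs in each trial arm". Section 6 defines the resource-use outcome by the same two items ("collected at 3 months of age on general practice visits and hospital admissions"), and the three-month data list in Section 9.6.3 repeats them ("Maternal and infant NHS healthcare resource use: collected on general practice visits and hospital admissions").

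Beyond the trial period, Section 12.6 adds modelled infant "healthcare costs (or savings) associated with gastrointestinal illness, lower respiratory tract infection and acute otitis media" to one year, and "potential lifetime maternal healthcare costs (or savings) due to breast cancer". It names no other cost.

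**The concern.** The quantity to be weighed is the cost of delivering frenotomy, yet the stated rule for arm costs has no term for it. Almost all infants in one arm should have the procedure and few in the other, so the omission does not cancel between arms. Modelled savings from any gain in breastfeeding are priced, while the procedure that is meant to produce the gain is not.

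Cost-effectiveness is half of the trial's stated aim. An analysis that followed Section 12.6 literally would make frenotomy look less costly to the NHS than it is.

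**Working it through.** The protocol states no cost figure, so there is none to reproduce. The check compares the costing rule with what is delivered and recorded, and then sizes the gap in units of one procedure.

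**Is the frenotomy inside one of the two costed categories?** Section 10.1 describes a quick procedure under usual hospital practice, and Section 10.2 places the visit at a frenotomy clinic. Neither describes an admission, and it is not a GP visit. The resource-use items are also reported by mothers, whom Section 7 intends to keep masked, so a mother's report could not be relied on to carry the trial procedure.

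**What is recorded, and is it tied to costs?**

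| Item | Where recorded or defined | Named in the costing rule? |
|---|---|---|
| GP visits, hospital admissions | Sections 6, 9.6.3, 12.6 | Yes |
| Trial frenotomy and technique | Section 9.6.1, by the clinician on the day | No |
| Frenotomy in the comparator group; repeat frenotomy | Section 6, as outcomes; Sections 9.6.2 and 9.6.3 word the item as a request | No |
| Breastfeeding-support contacts | Sections 6 and 9.6.3 | No |

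**Size for the first procedure.** Let d be the proportion of the frenotomy arm who have it, c the proportion of the comparator arm who have it, and u the NHS cost of the procedure beyond what both arms receive. The rule as written omits, from the incremental cost per infant,

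(d - c) × u.

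- Inputs: c = 0.05 is the contamination limit in Section 7.1 and the allowance in Section 12.1. d = 1 (full delivery) is my assumption. u is not given.
- Result: (1 - 0.05) × u = 0.95u.
- As counts: 870 / 2 = 435 infants per arm. That is 435 uncosted procedures in one arm and 435 × 0.05 = 21.75, about 22, in the other. (435 - 21.75) / 435 = 0.95.

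**Sensitivity, still with d = 1.** The values of c other than 0.05 are assumed.

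| c | Omitted per infant |
|---|---|
| 0 | 1.00u |
| 0.05 | 0.95u |
| 0.10 | 0.90u |
| 0.20 | 0.80u |

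Incomplete delivery lowers the multiple one for one. Privately paid frenotomies are not NHS costs. If all of the 5% were private, the NHS difference would be the 1.00u in the first row.

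**What u contains.** Under Sections 7 and 10.2, comparator infants also attend the clinic, are shielded as though treated, and have an observed feed and advice. Those elements are common to both arms, so u is less than the cost of a whole procedure visit.

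**Direction, item by item.**
- Trial procedure: (d - c)u is positive whenever d exceeds c, so the frenotomy arm's incremental cost is understated.
- Rescue frenotomy in comparators: leaving it out understates the comparator arm's cost. The 0.95 already nets this off at 5%.
- Repeat frenotomy and extra support: the sign depends on which arm uses more, and the protocol gives no basis for predicting that. The minimum support is the same in both arms and cancels.

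**The case against.** The strongest reply is that Section 12.6 is silent on intervention cost rather than excluding it. The two categories describe what mothers report through the online platform. Delivery of the procedure reaches the database by another route, from the clinician. The objective expressly covers delivery resources, and a later analysis plan could add them.

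Part of this stands: the protocol nowhere says that frenotomy is excluded from costing, and a reader who infers a deliberate exclusion goes beyond the text. But Section 12.6 does more than list what mothers report. It says that these categories, once weighted, give the costs in each arm, and Sections 6 and 9.6.3 repeat the same list. A plan that followed the protocol would price the procedure at zero.

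Four stronger readings are tempting and are not supported:

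- **Every omitted item favours frenotomy.** This is shown only for the trial procedure. Rescue frenotomy works the other way, and support could go either way.
- **The bias can be stated in pounds.** No unit cost is given, and part of the clinic visit is common to both arms.
- **The results would show a false saving, in the cost-utility analysis too.** The main analysis is a cost-consequence analysis with costs and outcomes set out separately, and later frenotomies and support use are reported as outcomes even if unpriced. The cost-utility analysis takes the mother's perspective to three months, and the protocol does not say whether an infant procedure belongs in it.
- **A change of wording repairs everything.** That is nearly so for the trial procedure. For later frenotomies and support contacts, the protocol does not say that NHS provision is recorded separately from private or voluntary provision.

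**Conclusion.** The point holds for the trial frenotomy. The costing rule in Section 12.6 does not serve the protocol's own economic objective: as written, the procedure costs nothing in either arm, and the incremental NHS cost of the frenotomy arm is understated by up to about 0.95 procedure costs per infant. That figure assumes full delivery in the frenotomy arm and contamination at the planned 5%, all of it NHS-provided. It counts first procedures only, and it refers to cost beyond what both arms receive at the clinic.

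For rescue and repeat frenotomy and for support contacts, the finding is that they are not stated to be costed. Their net effect on the comparison is unknown. The flaw is confined to the economic evaluation and should be corrected before that analysis is run.

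**What to change.** State in Section 12.6 that the costs in each arm also include:

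1. the NHS-provided trial frenotomy, counted from the delivery data in Section 9.6.1;
2. any NHS-provided later first or repeat frenotomy;
3. NHS breastfeeding-support contacts, once two matters are settled. The counting window must be reconciled, because Section 6 counts from the trial procedure and Section 9.6.3 from first referral. NHS contacts must also be separated from private or voluntary ones, because contacts with any supporter are counted.

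Name the source of the unit cost for frenotomy, and limit it to cost beyond the visit elements shared by both arms. State also whether the infant's procedure enters the cost-utility analysis.

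For the trial procedure, the cost of the change is wording plus one unit cost to be sourced, since delivery is already recorded. Items 2 and 3 need a minor clarification of the follow-up questions: who provided the care, and whether a frenotomy was done or only requested. Randomisation, the sample size and the primary analysis do not change.

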13. DATA MANAGEMENT

13.1. Access to data

Direct access to the study data, source data and medical records will be granted to authorised representatives from the NPEU CTU, Sponsor and host institution for the purposes of monitoring, audit, or inspection of the study to ensure regulatory compliance. Staff will have authenticated and restricted access to the clinical database ensuring they are only able to see data on participants recruited at their Trust. Access to the electronic data is strictly controlled using individual passwords for all staff accessing the electronic databases.

13.2. Data recording and record keeping

Data on the primary and secondary outcomes will be collected by mother's self-report using a mobile phone, tablet, computer or by telephone, or extracted from hospital records by assessors blinded to treatment allocation, or by linkage to routine data, where possible, for longer-term outcomes. Text and/or electronic notification reminders for completion will be sent as appropriate, with the option for telephone completion in the event of a delayed response to ensure a high response rate. The option for telephone completion will be available for mothers who do not have a smartphone, or who require translation, or who have other specific access needs which preclude the use of the online data collection platform.

Trial data will be collected using paper or electronic Case Report Forms (eCRFs) and automatically transferred for storage in the clinical database. The individual participant data will be identified by a study participant specific number only. A separate administrative database will be used to store the participant's name and any other identifying details. The two central databases will link the data by the participant's study number only, and are basted by the NSEU CTU on behalf of the Spensor. All data will be processed

in line with the NPEU CTU Data Management Standard Operating Procedures (SOPs). The Sponsor has delegated the responsibility for ensuring confidentiality of participant information to the NPEU CTU.

Archiving will follow the completion of the study and publication of results as detailed in NPEU SOPs and in line with NHS guidelines for a minimum of 25 years. At this point, the requirements to continue to archive these data will be reviewed in line with the applicable data protection guidelines. Electronic files will be stored on a restricted access (named individuals) server held in a secure location. In line with the NPEU CTU security policy, authorised access to the NPEU CTU is via an electronic tag entry system and individual rooms are kept locked when unoccupied. Authorised staff will process data via a secure network which requires individual login name and password. No data are stored on individual workstations. The data is backed up automatically overnight to an offsite storage area accessed by authorised personnel via electronic tag and key-pad systems.

All paper and electronic data will be stored securely in strict compliance with data protection regulations.

14. QUALITY ASSURANCE PROCEDURES

14.1. Monitoring

The PI will be responsible for the running of the trial at their site. This will include ensuring successful recruitment, staff education and training, and study data completeness and quality.

The NPEU CTU will develop an appropriate central monitoring plan for the trial, based on the risk assessment. Recruitment patterns at sites and within the data will be monitored. Any unexpected patterns, issues, or outlier data will be investigated and may trigger 'for cause' site monitoring. No other routine monitoring or auditing will be conducted unless the central monitoring triggers cause to do so.

14.2. Risk assessment

The trial will undergo a risk assessment prior to starting, which will be reviewed at regular intervals.

14.3. Project management

The study is sponsored by the University of Oxford. The trial will be run by the NPEU CTU, based at the University of Oxford, and the CI.

The trial will be run on a day-to-day basis by the Project Management Group (PMG), which reports to the Trial Steering Committee (TSC), which in turn is responsible to the NIHR HTA programme. The PMG will consist of the Chief Investigator, CTU Director, Senior Trials Manager, the Trial Statistician, the Quality Assurance manager and other project staff. The PMG will meet every month.

The Co-Investigator Group (CIG), an extended PMG, will comprise all members of the co-applicant group and the members of the PMG to review progress, troubleshoot and plan strategically.

The trial will be overseen by the Trial Steering Committee (TSC) which will have ultimate responsibility for considering and, as appropriate, acting on the recommendations of the DMC. The TSC will include an independent chair, at least two other independent members, PPI representative(s), and the Chief Investigator. The TSC will review the progress of the trial and report on progress to the funder. Observers from the HTA programme will be invited to attend all TSC meetings.

The Data Monitoring Committee (DMC), independent of the applicants and the TSC, will review the progress of the trial and interim analysis at least annually, and provide advice on the conduct of the trial to the TSC and (via the TSC) to the NIHR HTA programme.

15. ETHICAL AND REGULATORY CONSIDERATIONS

15.1. Declaration of Helsinki

The CI will ensure that this study is conducted in accordance with the principles of the Declaration of Helsinki.

15.2. Guidelines for Good Clinical Practice

The CI will ensure that this study is conducted in accordance with relevant regulations and with Good Clinical Practice.

15.3. Approvals

The protocol, informed consent form, PIL and any proposed advertising material will be submitted and approval will be obtained from an NHS Research Ethics Committee (REC), through the Health Research Authority (HRA) approval system. In addition, Trust Confirmation of Capacity and Capability will be obtained prior to any trial activity at that site.

The CI or their delegate will submit and, where necessary, obtain approval from the above parties for all substantial amendments to the original approved documents.

15.4. Reporting

The CI shall submit once a year throughout the study, or on request, an Annual Progress report to the REC Committee, HRA (where required) host organisation and Sponsor. In addition, an End of Study notification and final report will be submitted to the same parties.

15.5. Participant confidentiality

The trial staff will ensure that participant anonymity is maintained. All documents will be stored securely and only accessible by trial staff and authorised personnel. The trial will comply with data protection regulations, which require data to be anonymised as soon as it is practical to do so.

15.6. Expenses and benefits

No financial or material incentive or compensation will be provided to parents for enrolling their infant in this trial.

15.7. Other ethical considerations

Parents will be asked to consent for inclusion of their infants into the trial on the basis that they will be masked to intervention allocation. Parents will therefore need to be adequately advised on how to respond in the event of post-frenotomy adverse events such as bleeding, as well as what to do in the event of ongoing feeding difficulties. In order that parents are able to rapidly seek advice in the event of post-frenotomy adverse events (in the group that undergo frenotomy) or rapidly obtain further advice in the event of ongoing feeding difficulties (both groups) with recourse to rescue frenotomy or repeat frenotomy if necessary, both groups will be provided with standard post-frenotomy advice. Only sites with rapid access via drop-in clinic or telephone advice to breastfeeding support will be included in the study, and all parents will be given an appointment for at least one follow-up visit. All research midwives taking consent from parents will be trained in how to advise parents as to their actions in the event of either adverse events or ongoing feeding problems.

In order to maintain masking, infants may be taken into a separate room, where the frenotomy will be undertaken or not. This may be upsetting to both mother and infant. However, the infant will be returned to the mother after a few minutes of separation. Mothers will be made aware of this given the option to remain with their baby but will be asked not to directly observe the trial intervention in order to maintain blinding.

16. FINANCE AND INSURANCE

16.1. Funding

This trial is funded by the National Institute of Health Research (NIHR) Health Technology Assessment (HTA) programme (ref: 16/143/01). The views expressed are those of the author(s) and not necessarily those of the NHS, the NIHR, or the Department of Health.

16.2. Insurance

The University has a specialist insurance policy in place which would operate in the event of any participant suffering harm as a result of their involvement in the research (Newline Underwriting Management Ltd, at Lloyd's of London). NHS indemnity operates in respect of the clinical treatment that is provided.

16.3. Intellectual Property

Ownership of IP generated by employees of the University vests in the University. The protection and exploitation of any new IP is managed by the University's technology transfer office, Oxford University Innovations.

17. PUBLICATION POLICY

The success of the trial depends on a large number of midwives, neonatologists, obstetricians, paediatric surgeons, breastfeeding supporters and parents. Credit for the trial findings will be given to all who have collaborated and participated in the trial including all local co-ordinators and collaborators, members of the trial committees, the FROSTTIE Co-ordinating Centre and trial staff. Authorship at the head of the primary results paper will take the form "[name], [name] and [name] on behalf of the 'The FROSTTIE Collaborative Group'". The drafting of the paper will be the responsibility of a writing committee. Named authors will be listed in the following order: individual responsible for completing the first draft of the paper, lead analyst, all other members of the writing committee in alphabetical order, lead supervising author. All other contributors to the study will be listed at the end of the report, with their contribution to the study identified.

Those responsible for other publications reporting specific aspects of the study, such as the economic evaluation, may wish to utilise a different authorship model. Decisions about authorship of additional papers will be discussed and agreed by the trial investigators and the TSC.

Parents will be sent a summary of trial publications if they wish, which will contain references to full papers.

